### **DATA ANALYSIS**

We will use generalized estimating equations (GEE) with robust standard error estimates to model within-subject and between-group differences over time. First we will investigate whether an unstructured correlation matrix is best fitting for the error term based on examination of the working correlation matrix output. If an exchangeable structure fits the data, we will consider using a random-effects mixed model with restricted maximum likelihood, due to its weaker assumption for missing data on the response variable. Using either approach, of primary interest will be the group (drug treatment) by time interaction, which will tell us whether the change in the dependent variable over time differs between groups. We will include as covariates any pre-treatment variables (e.g., demographics, baseline levels of the dependent variable, comorbidities, laboratory test values) that differ between groups even at a trend level of significance ( $p < .10$ ).

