### 3 STUDY OBJECTIVES

#### **PRIMARY OBJECTIVE: CELLULAR BIOMARKER OF ENDOTHELIUM**

The primary objective is to ascertain if 16 weeks of Dapa or Dapa+Saxa Combo therapy will improve :

CD34+ cell number,  
CD34+ migratory function and  
CD34+ gene expression in type 2 diabetes with CVD.

*Please see appendix A for the primary objective laboratory protocol.*

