## **9 STATISTICAL & DATA ANALYSIS**

### **STATISTICAL ANALYSIS**

Sandri et al. (2005, Study A, patients with peripheral arterial occlusive disease) found that in the control group, CD34+ cells increased from 372 cells per mL blood at baseline (SD 156) to 402 (SD 183) at 4 weeks. In their exercise training group, the increase was from 458 (SD 252) at baseline to 2977 (SD 852) at 4-weeks. We created a simulated data set with these parameters in order to calculate the percent of CD34+ cell variation that was explained by the group x time interaction. We tested two random effects mixed models, one without and the other with, a group x time interaction (group is treatment vs control; time is pre vs. 4-weeks post). The percent variance explained =  $(V_{no-int} - V_{int})/V_{no-int}$ , where  $V_{no-int}$  is the residual covariance parameter estimate without a group x time interaction term in the model, and  $V_{int}$  is the residual covariance parameter estimate with a group x time interaction term in the model. We found that based on the baseline and 4-week mean and standard deviation of CD34+ cell concentrations reported by Sandri et al., the interaction explained 84.5% of the variance in CD34+ cell concentration (a very large effect size). The correlation among repeated measures was  $r=.62$ . Using these parameters in G-Power3 (version 3.1.3), with 2 groups measured at 2 time points, in order to achieve power  $>.95$  would require a total sample size of 6 subjects (3 per group) each measured at 2 time points. If the group x time interaction explained only 50% of the variance in CD34+ cell count (still a large effect), we would need sample size of 8 (4 per group) in order to achieve power  $>.95$ , if only two groups are present.

In another study, Sen et al., in a sample of patients with pre-diabetes (n=11), CD34+ cell number increased from 0.8 (SEM 0.1) before exercise, to 1.4 (SEM 0.2) after exercise, a pre-post effect size (Cohen's d) of 1.81.

Taking multiple study observation factors, in order to detect an effect of this size using a 2-tailed paired t-test, with alpha=.05, for power  $>.95$ , the number of subjects required would be 7-8, per group.

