However, these two quoted studies are different from our proposed study on patients with diabetes. It is well known that diabetes can affect CD34+ number and function, therefore in our proposed study the number of CD34+ cells available from the subjects may be a limiting factor. *Therefore, we propose to enroll 45 and retain 36 patients (10 subjects per group), in order to safely determine the effect of two individual groups of Dapa alone and Dapa+Saxagliptin combination with adequate number of CD34+ cells available for all proposed cellular outcome measures.*

Power calculation based on Sandri et al emphasizes CD34+ cell number and our recent study which looked at one of the medications being tested in this current combination protocol [41] takes into consideration CD34+ cell function and gene expression which verified our current statistical calculation. Our study actually demonstrated the validity of CD34 function and gene expression measures which were statistically significant.

However, this current study protocol describes a different cohort than Dore/Domingues et al [41] and similar to cohort described in Sandri et al (that is subjects with CVD). Currently there is no published study on progenitor cells looking at SGLT-2 inhibitor or in combination with a DPP4 inhibitor that we can base our calculations on and the closest will be our published study. [41].

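### The lead GEE analysis names no small-sample correction at 10 to 15 patients per arm; in its ordinary form a nominal 5% test of one week-16 arm contrast runs at 7 to 8%, and joint interaction tests run higher

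*Combined protocol and SAP*

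**What the plan says.** The lead method is in Section 9, Data Analysis: "We will use generalized estimating equations (GEE) with robust standard error estimates to model within-subject and between-group differences over time". The target follows: "Using either approach, of primary interest will be the group (drug treatment) by time interaction". A second model is held in reserve: "If an exchangeable structure fits the data, we will consider using a random-effects mixed model with restricted maximum likelihood". Covariates are to be added by a screen for baseline imbalance: "We will include as covariates any pre-treatment variables (e.g., demographics, baseline levels of the dependent variable, comorbidities, laboratory test values", at p < .10.

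Nothing in Section 9 or elsewhere says which sandwich estimator is meant, whether Wald statistics are referred to z, t, chi-square or F, how degrees of freedom are obtained under either model, or whether visit is categorical or linear.

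Enrolment is 15 per arm. Retention is 12 per arm in the synopsis and Section 4 but 10 in the Study Design Overview. Section 9, Statistical Analysis, carries both figures: "we propose to enroll 45 and retain 36 patients (10 subjects per group". Outcomes are measured at weeks 0, 8 and 16. The primary objective in Section 3 is an arm question at a fixed time: "The primary objective is to ascertain if 16 weeks of Dapa or Dapa+Saxa Combo therapy will improve" CD34+ cell number, migratory function and gene expression.

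**The concern.** The robust sandwich is justified for a large number of independent subjects. Here each arm comparison rests on 20 to 30 patients. At that size the uncorrected sandwich is too small on average, and the normal or chi-square reference ignores the uncertainty in it. Both errors act in the same direction: p-values too small and intervals too short.

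If a drug has no effect on an outcome, a comparison read at the 5% level would then give a false positive about once in 13 to 15 times instead of once in 20. The same applies to each outcome analysed this way. Joint tests estimate more covariance terms from the same few patients, so they are affected more.

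**Working it through.** **Inputs.** Patients per arm n = 10, 12, 15 (Section 4; Section 8, Study Design Overview; Section 9). Three arms, three visits. Correlation among repeated measures .62 and two-sided alpha .05, both taken from the sample-size text in Section 9. Assumed, not in the documents: normal outcomes, equal spread across arms, complete data, and a model with a mean for every arm at every visit.

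**The plan's own figure.** The plan gives no error rate for the GEE. Its nearest calculation is the paired t-test with d = 1.81, from 0.6/(0.1 × √11). Noncentral-t power is 93.8% at n = 6, 97.6% at 7 and 99.1% at 8, so the stated 7-8 per group for power above .95 reproduces. That calculation uses a t reference; the planned analysis names none.

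**Single week-16 contrast.** Under the model above, the GEE estimate is the difference between two arms in mean change from baseline. Each arm's ordinary sandwich variance is (s²/n) × (n-1)/n, where s² is the usual sample variance of change. The Wald z is therefore the two-sample t multiplied by √(n/(n-1)), and the true rejection rate is

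P(|t(2n-2)| > 1.96 × √((n-1)/n)).

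| n per arm | threshold applied to t | df | true rate | correct threshold |
|---|---|---|---|---|
| 10 | 1.859 | 18 | 7.9% | 2.101 |
| 12 | 1.877 | 22 | 7.4% | 2.074 |
| 15 | 1.894 | 28 | 6.9% | 2.048 |

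Actual coverage of the 95% interval is the complement: 92.1/92.6/93.1%. Direct simulation agrees (8.0/7.4/6.9%). Fitted GEE models with exchangeable working correlation gave 7.3/7.1/7.0% in 2,500 runs each (Monte Carlo error about 0.5 points).

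**Joint tests, by simulation, uncorrected sandwich with chi-square.** Week-16 test on 2 df: about 10/9/8%. Full interaction on 4 df with categorical visits: about 16/13-14/12%.

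**After correction, equal spread.** In this setting Kauermann-Carroll multiplies the variance by n/(n-1), giving s²/n. With Satterthwaite df the contrast then runs at 4.8-5.0%. Mancl-DeRouen multiplies by (n/(n-1))². With t(2n-2) the rate is P(|t| > t.975 × √(n/(n-1))) = 4.0/4.1/4.3%, slightly conservative. The 4-df test with Mancl-DeRouen and F(4, 3n-9) runs at 5.6-5.9%.

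**Stress case for unequal spread.** The cited exercise study reports "the increase was from 458 (SD 252) at baseline to 2977 (SD 852) at 4-weeks" in trained patients; in controls, "CD34+ cells increased from 372 cells per mL blood at baseline (SD 156) to 402 (SD 183) at 4 weeks". With r = .62 the SDs of change are √(252² + 852² - 2 × .62 × 252 × 852) = 723 and √(156² + 183² - 2 × .62 × 156 × 183) = 150. Setting 723 in both active arms and 150 in placebo:

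- Kauermann-Carroll contrasts stay at about 5%.
- The corrected 4-df test runs at about 7-9%.
- A mixed model with one variance shared by all arms runs at about 10.7% for combination versus dapagliflozin alone (about 9% at an SD ratio of 2).

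**Cost.** Interval width relative to the uncorrected analysis is (t.975/1.96) × √(n/(n-1)) = 1.13/1.11/1.08 for Kauermann-Carroll, taking t on 2n-2 df, and (t.975/1.96) × n/(n-1) = 1.19/1.15/1.12 for Mancl-DeRouen. Power for a true difference of 1 SD of change (noncentrality √(n/2)) is 65/72/80% uncorrected, about 56/64/75% with Kauermann-Carroll and 52/62/73% with Mancl-DeRouen and t. An exact 5% t-test gives 56/65/75%.

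**The case against.** The plan is silent rather than wrong. It does not forbid a corrected sandwich, and a robust score test or the REML model would largely remove the inflation when spread is equal. The exchangeable r = .62 used above is also the condition under which REML would be considered. This stands in part: the rates describe the ordinary reading of the words, not a declared choice. But REML is only to be considered, carries no degrees-of-freedom method, and is not safe by default if spread differs between arms.

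The single contrast is not the plan's named test. That is correct, and three stronger readings should be resisted:

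- A reader might infer that week-16 contrasts ought to become the primary tests, with the interaction demoted. A standard-error correction does not need this. It would set aside what Section 9 calls of primary interest and add primary comparisons with no multiplicity rule.
- A reader might infer that the trial will run at 12-16%. Those rates need categorical visits and a joint 4-df Wald chi-square test, neither of which is stated.
- A reader might take the rates for active versus placebo with SDs 723 and 150 (9.3/8.5/7.6% uncorrected) as expected. They come from an exercise arm whose mean rose from 458 to 2977. A drug with no effect would not be expected to raise the spread that far, and Section 9 itself says the cited studies differ from this trial. They are a stress case only.

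Finally, an excess of 2 to 3 points in a 45-patient biomarker study is modest. That bears on priority, not on whether to repair it.

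**Conclusion.** The concern holds. The stated lead method, in its ordinary form, does not hold its 5% level at this trial's size: 7.9/7.4/6.9% for one week-16 contrast, about 10/9/8% on 2 df, and about 16/13-14/12% on 4 df if visits are categorical, at 10/12/15 per arm. The intervals are correspondingly short. The single-contrast rates are exact under normality, equal spread and complete follow-up; the joint rates are simulated under the same assumptions. The omission should be fixed before unblinding; it does not invalidate the design. Multiplicity across arms and outcomes is a separate matter, as is the conflict between 10 and 12 retained per arm, which needs reconciling.

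**What to change.** Keep GEE, and keep the group-by-time interaction as the test of primary interest. Add to Section 9, Data Analysis:

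> Robust standard errors will use a small-sample bias-corrected sandwich. The joint group-by-time test will use the Mancl-DeRouen sandwich with an F reference. Arm contrasts within the interaction will use the Kauermann-Carroll sandwich with Satterthwaite degrees of freedom, or Mancl-DeRouen with a t reference for count outcomes. If the REML mixed model is used, Kenward-Roger or Satterthwaite degrees of freedom will be used, with covariance allowed to differ by arm.

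State also whether visit is categorical, and the F denominator; the 4-df figures above use patients minus 9. Mancl-DeRouen is suggested for counts, such as the colony assay in Appendix A, because under assumed means of 5 or 20 and between-patient coefficients of variation of 0.4-0.8 it ran at 4.2-6.1%, against 5.1-7.2% for Kauermann-Carroll. Those inputs are not in the documents.

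The cost is a few sentences and standard methods, with no new data. Arm-contrast intervals widen by 13/11/8% with Kauermann-Carroll, or 19/15/12% with Mancl-DeRouen and t. The loss of power comes mostly from restoring the 5% level: nearly all of it with Kauermann-Carroll, about two thirds with Mancl-DeRouen. The correction is not complete for the joint test, which would still run at about 7-9% if spread differed strongly by arm; the report should say so.

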## 4 INVESTIGATIONAL PLAN

### STUDY DESIGN AND DURATION

#### Enroll n=45 (15/group) for evaluable n=36 (12/group)

#### **+/- 6 day window for visits**

\*Assessed at week 0, 8 and 16: Primary, Secondary & Tertiary Outcomes.

Week 20: A telephone call to subjects will be made 4 weeks after last dose of study medication to determine if there have been any adverse events.

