**Weeks 0, 8 and 16 (Visits 1-3):** Subjects will all have the same measurements and will continue on study medication or placebo. All primary and secondary measures as outlined before will be carried out.

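### The primary group-by-time interaction spans weeks 0, 8 and 16, but the plan fixes neither the coding of time nor the deciding visit, so the test need not address the 16-week objective

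*Combined protocol and SAP*

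**What the plan says.** Section 3 (Primary Objective) ties the question to a treatment duration: "The primary objective is to ascertain if 16 weeks of Dapa or Dapa+Saxa Combo therapy will improve" CD34+ cell number, migratory function and gene expression. The Synopsis and the Outcomes part of section 8 repeat the 16 weeks.

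Section 4 (Study Design and Duration) sets the visits: "Assessed at week 0, 8 and 16: Primary, Secondary & Tertiary Outcomes". The Study Design Overview in section 8 confirms that the same measurements are taken at all three.

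Section 9 (Data Analysis) describes the model: "We will use generalized estimating equations (GEE) with robust standard error estimates to model within-subject and between-group differences over time". On the correlation, "First we will investigate whether an unstructured correlation matrix is best fitting for the error term"; if an exchangeable structure fits, a random-effects mixed model may be used. Then: "of primary interest will be the group (drug treatment) by time interaction, which will tell us whether the change in the dependent variable over time" varies by arm.

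Section 9 (Statistical Analysis) bases its interaction power calculation on a pre/post design, "with 2 groups measured at 2 time points".

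No section names a week-16 contrast, restricts the interaction to weeks 0 and 16, gives week 8 a supporting role, or says how time enters the model.

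**The concern.** With two visits, the group-by-time interaction and the comparison of end-of-treatment change are the same test. With three visits they are not. A categorical interaction over three arms and three visits has (3-1) x (3-1) = 4 degrees of freedom. It asks whether the arms differ in change at week 8, at week 16, or both, and rejecting it does not show that they differ at week 16.

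Two consequences follow if visit is categorical. A shift at week 8 that has gone by week 16 can produce a significant result on the test of primary interest. And an effect that grows towards week 16 is spread over a 4-df test, with less power than a direct week-16 comparison.

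If time is linear, the same sentence describes a different hypothesis, about slope. Nothing in the plan settles which one is meant before unblinding.

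**Working it through.** **Inputs from the documents.** Three arms; visits at weeks 0, 8 and 16; correlation .62 (section 9, from the two-time-point calculation); two-sided alpha .05 (section 9, given for the paired t-test); 12 evaluable per arm (Synopsis, section 4) or 10 (Study Design Overview; section 9 also gives 10 per group), so both are run.

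**Assumptions not in the documents.** Normal data, SD 1 at each visit, exchangeable correlation at .62, no missing data, both active arms shifted equally from placebo, effect sizes as shown.

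**The plan's own figures.** d = 0.6/(0.1 x √11) = 1.81. Paired t-test power is .976 at n = 7 and .991 at n = 8, so 7-8 per group reproduces. For the 2 x 2 interaction, using G*Power's default effect-size convention, power exceeds .95 at the stated totals of 6 and 8. These figures are not in question here; they concern two time points.

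**Closed-form check, visit categorical (mixed-model F, exchangeable).** The noncentrality is λ = n x Σ(arm deviations²) x Σ(visit deviations²)/(1-ρ). For arms (1, 1, 0) the first sum is 2/3.
- Week 8 only, profile (0, 1, 0): the visit sum is 2/3. At n = 12, λ = 12 x 2/3 x 2/3/0.38 = 14.04, and F(4, 66) rejects in 84%. At n = 10, λ = 11.70, giving 75%.
- Full effect from week 8, profile (0, 1, 1): the visit sum is again 2/3, so λ and the rejection rate are unchanged. The test cannot tell this pattern from the transient one.
- Build-up, profile (0, 0.5, 1): the visit sum is 1/2. At n = 12, λ = 10.53, giving 71%.

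**Week-16 change.** Variance of change = 2(1-.62) = 0.76.
- Difference of 1.0 SD, n = 12: three-arm F has λ = 12 x (2/3)/0.76 = 10.53 on (2, 33) df, power 80%. One active-versus-placebo contrast has noncentrality 1/√(0.76 x 2/12) = 2.81 on 33 df, power 78%.
- Week-8-only effect: λ = 0, so rejection is 5%.

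**Simulation, visit categorical, unstructured covariance (exact Wilks F on the two change scores, 20,000 trials per setting).** It rejects in 5% when there is no effect.

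| True pattern (SD) | Interaction, n=12 | Interaction, n=10 | Week-16 comparison, n=12 | Week-16 comparison, n=10 |
|---|---|---|---|---|
| 1.0 at week 8 only | 81% | 71% | 5% | 5% |
| 0.8 at week 8 only | 59% | 50% | 5% | 5% |
| 0.5 at week 8 only | 25% | 21% | 5% | 5% |
| 0.5 at week 8, 1.0 at week 16 | 67% | 57% | 78-80% | 70-71% |
| 1.0 at weeks 8 and 16 | 81% | 71% | 78-80% | 70-71% |

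**Robust GEE Wald test, no small-sample correction.** For 1.0 SD at week 8 only it rejects in 90% (n = 12) and 86% (n = 10). It also rejects in 13% and 16% with no effect at all, so part of that excess is inflation of the test itself.

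**Linear time.** With equally spaced visits and complete data the slope contrast is (-1, 0, +1), so week 8 has zero weight. In a random-intercept model with n = 12, the 1.0 SD week-8-only effect gives about 0.9% rejection; this falls below 5% because the unmodelled bump enters the residual. The build-up effect has about 82% power, slightly above the week-16 comparison. With the robust GEE the week-8-only rejection stays at that test's null level of 9%.

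**The case against.** The strongest reply is that both harms depend on a coding the plan never chose. Describing the interaction as change over time, and allowing a random-effects model, fits linear time as well as categorical visits; the unstructured correlation matrix suits discrete visits but does not settle it. This stands, and it is why the point is stated conditionally. It does not remove the gap: one sentence allows two tests, and for the same transient effect they reject in 81% and about 0.9% of trials.

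A reader might infer that the trial will be declared successful on week 8 alone. The documents do not support that. The interaction is called the item of primary interest; no success rule is attached to it, and an interaction driven by week 8 would not on its face answer an objective about 16 weeks of therapy.

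Nor do the documents predict a transient effect. Treatment continues to week 16, and the Background's argument for a fast CD34+ response, with gene expression changing within two weeks, is equally compatible with an early effect that persists. In that case the two tests have similar power. For smaller transient effects the problem shrinks, to 25% at 0.5 SD with 12 per arm.

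Finally, the two-time-point power basis is a mismatch with the three-visit analysis, but it does not show that the stated sample sizes are wrong.

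**Conclusion.** The point holds as an underspecification of the main test: time coding and deciding visit are both missing, and the objective is tied to 16 weeks. If visit is categorical, the consequence is material. A week-8-only effect of 0.5 to 1.0 SD makes the interaction significant in 25% to 81% of trials at 12 per arm (21% to 71% at 10), against 5% for a week-16 comparison, and power for a building effect is 67% against 78-80%. If time is linear with complete data, neither harm arises.

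The percentages rest on normal complete data, equal SDs, a correlation carried over from two visits to three, assumed effect sizes, and an exact F test in place of the robust GEE that the plan names first. They show the direction and rough size of the problem and do not forecast this trial's result.

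**What to change.** In section 9 (Data Analysis), replace the sentence on the interaction with wording to this effect: visit enters the model as a categorical factor; the primary test is the between-group difference in change from week 0 to week 16, estimated from the longitudinal model using all visits; the week-8 difference and the overall group-by-time interaction are supportive. Week-8 data stay in the model and still help where week-16 values are missing.

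The change needs no new patients, visits or assays. It has two costs. A transient week-8 effect no longer counts as a primary result. And if the effect is already complete at week 8 and flat afterwards, power changes by about 0-3 points against the exact F test (81% to 78-80% at 12 per arm; 71% to 70-71% at 10). Against the exchangeable mixed-model F at 12 per arm, the difference is 84 - 80 = 4 to 84 - 78 = 6 points.

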### **METHOD OF ASSIGNING SUBJECTS TO A TREATMENT**

Subjects, as per selection criteria below will be randomized to treatments using a permuted block design, developed by the Epidemiology & Biostatistics Research Core. This approach ensures groups will be approximately balanced at any time during the study and at study completion. Randomization will be performed by the MFA IDS Pharmacy staff who never come in contact with subjects.

The recommended dose of Dapagliflozin is 10 mg PO will be given once daily in the Dapa group. The recommended dose of Saxagliptin 5mg along with Dapagliflozin 10 mg (one of each) will be given PO once daily in the Dapa+Saxa Combo group. Saxagliptin should be administered once daily with or without food, at any time of day. Dapa should be administered once daily with food, **in the morning**.

*Because of this, all subjects will be instructed to take their medication once daily in the morning with food, as we will not know which subjects will be in the Dapa, Dapa+Saxa Combo, or placebo group.*

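### Covariates, including each outcome's own week-0 value, are chosen by testing randomised arms at p < .10, so covariate adjustment for baseline follows chance imbalance and may not correct it

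*Combined protocol and SAP*

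**What the plan says.** The covariate plan is one sentence at the end of Data Analysis in section 9. Pre-treatment variables enter the model if they are flagged by a between-group test at p < .10; the examples are demographics and "baseline levels of the dependent variable, comorbidities, laboratory test values) that differ between groups even at a trend level of significance". No covariate is fixed in advance and no other route into the model is given. The screening test (overall or pairwise) is not named. Nor does the plan say whether a flagged variable enters as a main effect or with a time interaction.

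The model is GEE with robust standard errors, or possibly a REML mixed model if an exchangeable structure fits. The order of work is: "First we will investigate whether an unstructured correlation matrix is best fitting for the error term". The contrast of interest is group by time, "which will tell us whether the change in the dependent variable over time differs between groups".

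Three other places matter. Section 6 says subjects "will be randomized to treatments using a permuted block design". Section 4 schedules the outcomes thus: "Assessed at week 0, 8 and 16: Primary, Secondary & Tertiary Outcomes". Neither section 4 nor section 9 says whether visit is a factor or a linear term in the trial analysis, or whether week 0 stays among the responses once baseline is also a covariate.

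**The concern.** Under randomisation, a p < .10 baseline difference is a chance event. The screen therefore selects variables by the size of an accidental gap, not by how well they predict the outcome. An outcome's week-0 value will often be its best predictor, yet it gets no standing of its own.

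Two things are at stake. First, the model for each outcome is settled only after its baseline data have been seen, and by a test that the plan does not name, so readouts belonging to one primary objective could be modelled differently by chance. Second, when a gap does appear, the reader will assume that adding the covariate dealt with it. On one natural reading of the plan it does not.

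**Working it through.** The plan gives no figure for how this rule behaves, so there is none to reproduce. The inputs are below; both 12 and 10 per arm were used because the document gives both.

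- Threshold p < .10, three randomised arms (sections 9 and 6).
- r = .62 among repeated measures (Statistical Analysis, section 9).
- Exercise-training study, controls: "CD34+ cells increased from 372 cells per mL blood at baseline (SD 156) to 402 (SD 183) at 4 weeks".
- Same study, trained group: "the increase was from 458 (SD 252) at baseline to 2977 (SD 852) at 4-weeks".
- Pre-diabetes study, n = 11: "CD34+ cell number increased from 0.8 (SEM 0.1) before exercise, to 1.4 (SEM 0.2) after exercise". SD = SEM × √11, so the baseline SD is 0.332. The plan's own d of 1.81 is recovered as 0.6/0.332. The follow-up to baseline SD ratio is 2. That r = .62 applies here is an assumption.
- Equal SDs at baseline and follow-up: an assumption, shown for range.

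**1. How often own baseline enters.** In simulated null trials, one overall F test flags 10%. Any of three pairwise t tests flags about 23%. Appendix A lists 4 + 5 + 4 + 2 + 3 = 18 genes. The expected number flagged is 18 × 0.100 = 1.8, or 18 × 0.226 = 4.1.

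**2. What entry does.** A baseline main effect is constant across a patient's visits, whereas group by time is a within-patient comparison. In exchangeable GEE fits with weeks 0, 8 and 16 as responses, visit as a factor and complete data, adding it moved the estimate by less than 1e-14 SE and left the robust SE unchanged (ratio 1.00). In one example data set with an imposed baseline gap, group by time was −0.377 (SE 0.347) with and without the covariate, while week-16 ANCOVA gave −0.047 (SE 0.310). With linear time and an unstructured correlation the estimate can move.

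**3. Size of the uncorrected offset.** At 12 per arm, a gap that just reaches p = .10 is t(.95, 22) × √(2/12) = 0.70 baseline SD. Change scores subtract baseline with slope 1, so the higher-baseline arm's contrast shifts by 0.701 × (slope − 1), where slope = r × SD ratio:
- equal SDs, slope .62: −0.27 SD;
- control SDs, slope .62 × 183/156 = .73: −0.19 baseline SD;
- pre-diabetes, slope 1.24: +0.17 baseline SD.

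**4. Type I error of the change contrast (t test of one pair) in flagged trials**, r = .62, 10–12 per arm, the same SDs in every arm:

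| SDs | That pair flagged | Overall test flagged | Any pairwise flagged |
|---|---|---|---|
| Equal (assumed) | 12% | 9–10% | 8% |
| Control, 156/183 | 8% | 7% | 6% |
| Pre-diabetes, ratio 2 | 6% | 5–6% | 5–6% |

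Over all trials, flagged or not, error is about 5%. ANCOVA in the flagged trials is also near 5%. With equal SDs and that pair flagged, error is about 18% at r = .3 and 9% at r = .8.

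**5. Precision forgone by the change score at r = .62**, as 1 − Var(adjusted)/Var(change):
- equal SDs: 1 − 0.6156/0.76 = 19%;
- treated 252/852 versus control 156/183: pooled slope 1.717, 1 − 500450/545601 = 8%;
- pre-diabetes: 1 − 2.4624/2.52 = 2%.

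Estimating the slope inflates the adjusted variance by 1 + 1/31 (12 per arm) or 1 + 1/25 (10 per arm) when arms share the same SDs. Net gain from always adjusting is then about 16% (equal SDs) and −1% to −2% (pre-diabetes). For the treated-versus-control SDs, simulation with the slope pooled over three arms gives 3–4%.

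**The case against.** The strongest reply is that the planned contrast already handles baseline. With week 0 as a response, group by time compares change from baseline for every outcome, whether or not the screen fires. That stands. A reader might infer that the 90% or so of unflagged outcomes would ignore baseline; the documents do not support this. What depends on chance is ANCOVA-type adjustment only. It also follows that, where a flagged baseline enters as a main effect with visit as a factor, having some genes adjusted and others not alters no estimate. It matters only under the other forms of entry and time coding that the plan leaves open.

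A reader might also infer that the screen inflates the overall false-positive rate. It does not in these simulations: the change contrast is valid over all trials, and the excess appears only given a flagged gap. Nor does the 12% figure describe either screening rule as such; it applies when the particular pair being compared is flagged, and it needs equal SDs, which neither cited data set shows.

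Two further limits stand. The rule that unflagged variables stay out is inferred from the absence of any other route, not written. And the 5% figures come from t tests and ANCOVA. The planned GEE with uncorrected robust standard errors rejects in about 7–8% of null trials at this size, which is a separate matter.

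**Conclusion.** The concern holds in a limited form. Covariate adjustment for an outcome's own baseline is triggered by chance imbalance, in about 10% or 23% of outcomes depending on an unnamed test, and without regard to prognostic value. With week 0 as a response, visit as a factor and complete data, a main effect triggered this way does not correct the imbalance.

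The harm is modest. At r = .62, error given a flag is about 5–12% depending on the SDs and the screening rule, against about 5% with ANCOVA. The net precision effect of always adjusting runs from about +16% to −2%, and the larger gain rests on assumed equal SDs. These results assume normal outcomes and complete data. The r comes from a 4-week exercise comparison; the documents give no r or SDs for the 16-week drug outcomes. The case for change rests mainly on pre-specification and on validity when the arms are imbalanced, and less on precision. Minor to moderate priority.

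**What to change.** Delete the p < .10 sentence and state: *Every outcome model will adjust for that outcome's week-0 value regardless of observed imbalance; no covariate will be selected by testing baseline differences.*

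Then fix the form. Within the planned GEE, use weeks 8 and 16 as responses, visit as a factor, and baseline and baseline-by-visit as covariates. If weeks 0, 8 and 16 are all to be responses with a common week-0 mean, say that this is a REML mixed model with unstructured covariance in place of GEE.

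The cost is a few sentences in section 9 and one or two degrees of freedom, with a possible 1–2% loss of precision if baseline adds little beyond the change score. The first form also excludes patients with no post-baseline value. No new data are needed, because week-0 values are already collected.
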